Of note, the shifting of responsibility of documentation of the new standardized accept note will not supplant the current role of the accepting clinician to make the clinical decision on acceptance or rejection of the transfer request. As is currently done, the Access Center nurse and accepting clinician participate in a conference call with the transferring clinician such that either can ask questions (and the Access Center nurse can hear all the answers and document them in the accept note template). In this way, the Access Center nurse can ensure that the minimum necessary information is collected and documented, while also including additional clinical information requested by the accepting clinician.

Aim 3. Prospectively evaluate the impact of the intervention on patient safety outcomes, including: clinician-reported medical errors and adverse events, length of stay after transfer, rapid-response or code within 6-hours of transfer, ICU-transfer within 24-hours of transfer, and 3-day and inhospital mortality.

Study Design: We will conduct a prospective 24-month interrupted time series (ITS) study during which we will implement the standardized accept note and evaluate impact on all measured outcomes post- versus pre-implementation, accounting for baseline temporal trends.

Setting, Subjects, Eligibility, Enrollment: Eligible patients will include any patient age 18 or older transferred from another acute care hospital to the GMS, cardiology, oncology or medical/cardiac ICU services at BWH during the study period. Because the intervention is not directly patient-facing, there will be no direct enrollment of eligible patients, and we will be requesting a waiver of written informed consent for patients (see Organizational Internal Review Process, above). Thus, all eligible patients transferred during the study period will be in the study.

Instruments, Tests and/or Measurements: A trained research assistant (RA) will conduct surveys of admitting clinicians within 48-hours after IHT patient admission to obtain clinician- reported medical errors and adverse events, including medical errors resulting in patient harm (e.g., preventable and

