8) Mortality, including 3-day mortality (within 3 days of transfer) and inhospital mortality (secondary outcome)

9) Intermediate process outcomes, including presence, timeliness and completeness of accept note as measured by frequency of accept note availability at time of IHT patient arrival and frequency of inclusion of prespecified data elements (secondary outcome)

Statistical Methods and Analytic Plan: All outcomes will be compared postversus pre-implementation via ITS methodology, allowing us to evaluate for statistically significant changes in outcomes while accounting for baseline trends. Multivariable analyses will be utilized to adjust for potential confounders.

Covariates: Potential confounders will be collected via administrative sources and include basic patient demographics (age, gender, race, ethnicity), insurance, diagnosis category (using standard ICD-10 grouper algorithms on the principal problem on the Hospital Problem List on admission, which we have found to be more accurate than the billing diagnosis on admission), comorbidity (i.e., Elixhauser score), illness severity (eCART score on admission, which uses vital sign and laboratory data to predict cardiac arrest, ICU transfer, or death among hospitalized patients),36 clinical service at time of admission, and time of year of transfer (by quarter) to adjust for training effects on residents and seasonal case mix. To avoid over-testing, all patient characteristics will be entered into the analysis model. Nonsignificant collinear terms will be removed from the final models.

Subgroup analysis: We will conduct a limited number of a priori subgroup analyses to evaluate for differential effect of the intervention in different sub-populations of transferred patients by using interaction terms (subgroup*intervention) to determine effect modification. Specifically, we will stratify analyses by: 1) admitting service (GMS, cardiology, oncology, medical/cardiac ICU); 2) diagnosis category; and 3) severity of illness on admission (using the eCART score as described above).

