Describe how risks to subjects are minimized, for example, by using procedures which are consistent with sound research design and which do not unnecessarily expose subjects to risk or by using procedures already being performed on the subject for diagnostic or treatment purposes.

Risks to subjects will be minimized by using procedures which are consistent with sound research design. Neither patients nor providers will be unnecessarily exposed to excess risk. The designed intervention is a local quality improvement initiative, with input from key stakeholders involved in the inter-hospital transfer process, and, as stated above, is hypothesized to be an improvement to current practices.

Additionally, all collected data is secured within the password-protected REDCap ecosystem – REDCap is a secure web application for building and managing online surveys and databases. Thus risks to data breach/patient confidentiality will be minimized.

Describe explicitly the methods for ensuring the safety of subjects. Provide objective criteria for removing a subject from the study, for example, objective criteria for worsening disease/lack of improvement and/or unacceptable adverse events. The inclusion of objective drop criteria is especially important in studies designed with placebo control groups.

Ensuring safety of patient subjects: The intervention itself will rolled out on the specific study units (general medical, cardiology, oncology and medical/cardiac ICU services) as part of a quality improvement effort to change systems for best practice as described. We will conduct periodic data safety monitoring (see below) to ensure that the intervention is not causing harm (e.g., increased adverse events, prolonged length of stay). Additionally, all patient-level data will be kept within Partners firewall, with only approved study staff access, thus minimizing risk to patient confidentiality/data breaches.

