NOTE: When subjects are unable to give consent due to age (minors) or impaired decisionmaking capacity, complete the forms for Research Involving Children as Subjects of Research and/or Research Involving Individuals with Impaired Decision-making Capacity, available on the New Submissions page on the PHRC website:

https://partnershealthcare.sharepoint.com/sites/phrmApply/aieipa/irb

For guidance, refer to the following Partners policy: Informed Consent of Research Subjects: https://www.partners.org/Assets/Documents/Medical-Research/Clinical-Research/Informed-Consent-of-Research-Subjects.pdf

DATA AND SAFETY MONITORING

Describe the plan for monitoring the data to ensure the safety of subjects. The plan should include a brief description of (1) the safety and/or efficacy data that will be reviewed; (2) the planned frequency of review; and (3) who will be responsible for this review and for determining whether the research should be altered or stopped. Include a brief description of any stopping rules for the study, when appropriate. Depending upon the risk, size and complexity of the study, the investigator, an expert group, an independent Data and Safety Monitoring Board (DSMB) or others might be assigned primary responsibility for this monitoring activity.

NOTE: Regardless of data and safety monitoring plans by the sponsor or others, the principal investigator is ultimately responsible for protecting the rights, safety, and welfare of subjects under his/her care.

The principal investigator and data analyst will review all complaints and adverse events reported from patient and provider subjects each quarter. These will be reported to the study sponsor and Partners IRB annually or immediately if the complaint or adverse event is serious. In addition, the principal investigator and data analyst will review on a monthly basis adverse event rates, hospital length of stay, and 7-day readmission rates to ensure that the intervention itself is not causing harm compared with the pre-intervention period. If an increase in harm is suspected, we will report it to the IRB and take action as needed. Given the minimal risk of this study, we are not planning any automatic stopping rules or using a DSMB.

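### The monthly harm review leaves out mortality, rapid response/code and ICU transfer, which the trial already collects as patient safety outcomes, so a rise in deaths could be missed

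*Protocol*

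**What the plan says.** The protocol's account of how patient subjects are kept safe promises: "We will conduct periodic data safety monitoring (see below) to ensure that the intervention is not causing harm". The examples of harm given there are more adverse events and longer stays. The detail follows under Data and Safety Monitoring, where the principal investigator and data analyst "will review on a monthly basis adverse event rates, hospital length of stay, and 7-day readmission rates". The stated purpose is "to ensure that the intervention itself is not causing harm compared with the pre-intervention period".

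The same section has a second strand. The same two people "will review all complaints and adverse events reported from patient and provider subjects each quarter", and these go to the sponsor and the IRB "annually or immediately if the complaint or adverse event is serious". Suspected harm is to be reported to the IRB and acted on. On formal oversight the section says "we are not planning any automatic stopping rules or using a DSMB".

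Aim 3 lists the patient safety outcomes. They include rapid response or code within 6 hours, "ICU-transfer within 24-hours of transfer, and 3-day and inhospital mortality". Under Instruments, Tests and/or Measurements, every outcome that does not come from the clinician survey is taken from administrative data. Seven-day readmission is not in the list of primary and secondary outcomes.

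**The concern.** The monthly review is the only stated comparison of rates with the pre-intervention period. It does not cover the gravest outcomes, although the trial collects them from the same source as length of stay, and the protocol gives no reason for reviewing one and not the others. The Background says that poor communication in these transfers leads to mis-triage and is associated with higher mortality. Early codes, ICU transfers and deaths are therefore where harm would be expected to show if the new documentation process worked badly.

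The measures that are reviewed do not fill the gap for deaths. A patient who dies early usually has a short stay, and one who dies in hospital cannot be readmitted. That leaves adverse event rates. Elsewhere in the protocol these come from a voluntary survey of the admitting clinician, aimed at 48 hours after admission and limited to harm due to medical care. Under Recruitment Procedures, a clinician who opts out is not approached again. A death that comes after the survey, or that the clinician does not attribute to care, would not be counted.

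**Working it through.** **Comparing the lists.** The protocol gives no figure for the safety review, so the first check sets the outcome list against the review list.

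| Measure | Trial outcome | Source | In monthly review |
|---|---|---|---|
| Adverse events | yes | clinician survey | yes |
| Length of stay | yes | administrative | yes |
| 7-day readmission | no | not stated | yes |
| Rapid response/code, 6 h | yes | administrative | no |
| ICU transfer, 24 h (non-ICU patients) | yes | administrative | no |
| 3-day and in-hospital mortality | yes | administrative | no |

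**Volume.** Power and sample size gives 1,848 transfers a year: 1,848 / 12 = 154 a month and 154 × 9 = 1,386 in nine months (the protocol prints 1,368; the difference does not matter here).

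**Assumptions, none from the documents.** Early deaths stay 2 days and all others stay S = 6, 8 or 10 days. Readmission is 8% of live discharges. Early mortality doubles from d0 to d1.

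**Length of stay.** The mean is 2d + S(1 − d), so the change is −(d1 − d0)(S − 2).

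| Early mortality | Deaths per month | Fall in mean stay, S = 6 / 8 / 10 |
|---|---|---|
| 2% to 4% | 3.1 to 6.2 | 0.08 / 0.12 / 0.16 day |
| 3% to 6% | 4.6 to 9.2 | 0.12 / 0.18 / 0.24 day |
| 5% to 10% | 7.7 to 15.4 | 0.20 / 0.30 / 0.40 day |

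The mean falls whenever the extra deaths have shorter stays than the other patients and nothing else changes. The fall is small. With an assumed standard deviation of 7 days, the standard error of a monthly mean is 7 / √154 = 0.56 day. Length of stay would give no warning, but it would not visibly improve either.

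**Readmission, 3% to 6%.**
- All transfers as denominator: 0.97 × 8% = 7.76% falls to 0.94 × 8% = 7.52%.
- Live discharges, extra deaths at average readmission risk: 8.00% before and after.
- Live discharges, extra deaths at an assumed 20% risk: (0.97 × 0.08 − 0.03 × 0.20) / 0.94 = 7.62%.

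The rate falls or stays the same, depending on a denominator that the protocol does not state.

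**Could a mortality review detect the change?**
- One month: an exact one-sided 5% test of 154 transfers against a known 2% needs at least 7 deaths (actual size 3.6%). Its power against 4% is about 42%.
- Nine months against nine months: about 28 versus 55 deaths (1,386 × 0.02 and 1,386 × 0.04). z = 0.02 / √[(0.02 × 0.98 + 0.04 × 0.96) / 1,386] = 3.09. Two-sided 5% power is Φ(3.09 − 1.96), about 87%.

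Monthly counts alone are weak. Cumulative counts are informative.

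**The case against.** The plan is not blind to harm. Adverse event rates come first in the monthly list and can rise with harm. The survey has two reminders and an in-person follow-up, and a 90% response is assumed. The monitoring section does not say that adverse event rates will come from the survey alone; that is inferred from how the rest of the protocol collects them. Quarterly review, immediate reporting of serious events and action on suspected harm stand beside the monthly review. The intervention is a note template and a change in who writes it, the accepting clinician still decides on the transfer, and the protocol calls the study minimal risk. A monitored measure need not be a trial outcome, so reviewing readmission is not in itself an error.

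All of this stands, and it rules out several stronger readings:
- A reader might infer that the review rests on length of stay and readmission alone, or that it is the only safeguard. The monitoring section contradicts both.
- A reader might infer that both measures improve when deaths rise. For readmission that is certain only with all transfers as denominator.
- A reader might infer that a doubling of mortality would go unseen. That requires none of the extra deaths to be reported as an adverse event, which nothing in the protocol shows.
- The masking argument concerns deaths. Nothing here shows that non-fatal codes or ICU transfers make the reviewed measures look better. For these two outcomes the point is only that they are collected and not reviewed.

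The objection does not explain the omission. Minimal risk may justify having no DSMB or stopping rule. It does not explain why a review already promised leaves out outcomes already collected. Reporting of individual events is not a comparison of rates.

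**Conclusion.** The point holds as a cheap improvement. The monthly comparison omits mortality, rapid response/code and ICU transfer, and the measures it does use cover deaths only in part: adverse events through survey response and attribution, length of stay in the wrong direction, readmission not at all for deaths in hospital. A rise in mortality could therefore be missed. The documents do not support saying that it would be.

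The omission is read directly from the text. The sizes are illustrations: every mortality, length-of-stay and readmission figure above is an assumption, and only the 1,848 transfers a year comes from the protocol.

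**What to change.** In Data and Safety Monitoring:
- Add 3-day mortality, in-hospital mortality, rapid response/code within 6 hours and ICU transfer within 24 hours (non-ICU patients) to the monthly review.
- Show each both by month and cumulatively against the pre-implementation period, because about 154 transfers a month give small counts.
- Show length of stay and readmission among patients discharged alive.
- State the denominator and data source for 7-day readmission.

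The cost is a few sentences, slightly more tabulation each month, and administrative data pulls on a monthly schedule. Apart from readmission, whose source is not stated, no new data item is needed.
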